12.5.4 Investigational Product

The investigational product will be assessed prior to insertion and after the removal from the bladder. The findings on the condition of the IP prior to insertion and after the removal will be presented in a listing.

12.5.5 **Pregnancy Test**

Pregnancy test results for patients will be provided in a data listing.

12.5.6 Urine Cytology

Urine Cytology test will be performed at screening. The results of this tests will be presented in patient listing.

12.5.7 Urine Culture

A listing of patient's urine culture results will be presented by treatment group and visit.

12.5.8 Suicidality Assessment

Not applicable.

12.5.9 **Potential Hy's Law**

Not applicable.

14.0 **INTERIM ANALYSIS**

Assuming that 5% of the randomized patients will not be evaluable for the primary analysis, to ensure that there are 72 evaluable patients approximately 76 patients will be randomized into the study. At a randomization ratio of 2:1:1, 72 evaluable patients ensures that there will be about 36 patients in the treatment group that gets two consecutive LiRIS 400 mg (LiRIS 400 mg/LiRIS 400 mg), 18 patients in the treatment group that gets Placebo and then LiRIS 400 mg (Placebo/LiRIS 400 mg), and 18 patients in the treatment group that gets two consecutive Placebo (Placebo).

15.0 **DETERMINATION OF SAMPLE SIZE**

A sample size of 36 patients in the LiRIS 400 mg/LiRIS 400 mg group versus 18 patients in the Placebo/Placebo group has 76% power to detect a difference of 1.152 in mean daily average bladder Pain NRS, assuming that the common standard deviation is 1.67 using a 1-sided two sample t-test with a type 1 error rate of 0.05. The calculation was performed using the commercial software **Example 1** The standard deviation assumption is based on the TAR-100-105 open label study, where the SD is the Week 4 Follow-Up raw average daily NRS.

17.0 DATA HANDLING CONVENTIONS

17.1 **VISIT TIME WINDOWS**

Table 17.1–1 presents, for both treatments periods, the derived visits for efficacy (excluding efficacy based on daily pain diary) and safety analyses and the corresponding range of study days (window) during which an actual visit may occur.

Following SDTM and ADaM standard, the date of first IP insertion will be considered as Treatment 1 Day 1. Similarly, the date of 2nd IP insertion will be considered Treatment 2 Day 1. However, in the assessment tables of the protocol and in Section 4 of this document and in the eCRF pages this is considered to be Treatment 1 Day 0 and Treatment 2 Day 0, respectively. For by visit analysis tables and listings the visit label will follow these protocol and eCRF visit definitions (3rd column in table 17.1-1). Some listing will also display study day using the SDTM definition. Hence, using SDTM and ADaM standards study day is calculated as follows (see 2nd column in Table 17.1-1):

Screening & baseline period (prior to IP insertion)

study day = visit date - 1st IP insertion date

Treatment 1 period :

study day = visit date - 1st IP insertion date +1

Treatment 2 Period :

study day = visit date - 2st IP insertion date +1

Throughout this document ,unless otherwise stated, this definition of study day is used.

27MAR2018 CSR 201025-001

If not stated otherwise, all by visit analysis will be using the visit windows specified above. The target day for each treatment period is referenced to days after first IP insertion within each treatment period. Treatment 1 Day 1 refers to the first IP insertion date while Treatment 2 Day 1 refers to the IP insertion date in Treatment 2 period. In contrast, if the assessment date is before date of Treatment 1 IP insertion, the study day is calculated as follows:

assessment date - date of Treatment 1 IP insertion.

The visit window for each treatment period is defined as follows:

[(target day of current visit + target day of previous visit)/2+1] to [(target day of current visit + target day of next visit)/2]

If a patient has 2 or more visits within the same visit window, the last visit with a nonmissing value will be used for the analysis.

For laboratory and vital signs analysis, baseline refers to study baseline, i.e. the baseline information collected at the start of Study 201025-001.

17.2 **DERIVED VARIABLES**

The data derivations and definitions listed in this section are to be applied to all analyses described in this analysis plan, unless otherwise stated.

- In this study there are two treatment periods:
 - Treatment period 1: for patients that just receive treatment in the randomized and blinded phase of the trial, it covers the period from the first Treatment 1 IP insertion to study exit. In contrast, for patients that receive IP insertions in both the randomized phase of the study (Treatment 1) and the open label phase of the study (Treatment 2) it covers the period from first Treatment 1 IP insertion up to Treatment 2 IP insertion,
 - Treatment period 2: covers the period from Treatment 2 IP insertion to study exit.
- Study days for each treatment period X (X=1 or 2) will be calculated as:
 - Study day of Treatment X = visit date (day 1 of Treatment X) + 1.
- The baseline value of an assessment will be the last value recorded prior to the patient being inserted with first Treatment 1 IP on Day 1.
- Unless otherwise stated no imputation will be performed for missing data. All analyses will be based on the observed data.
- For analyses that are by stratification factor, actual stratification levels rather than randomization stratification levels will be used.
- Data will be pooled across the investigational sites.
- Descriptive statistics for continuous/ordinal data include the sample size (N), mean, standard deviation (SD), median, minimum (Min), and maximum (Max) and 95% confidence intervals.
- Summary statistics for categorical variables include sample size (N), frequency count (n), and percentage (%).

17.2.1 **Pain Data Derivations**

A pain assessment tool will be utilized in the study to capture the average daily pain and the daily worst pain scores on an electronic hand held device. Patients will be asked to rate their daily pain on a pain NRS consisting of an 11 point integer scale ranging from 0 for "no pain" to 10 for "worst pain imaginable". The pain assessment will continue every day up to and including the day prior to the Exit visit.

The patient's baseline average daily pain NRS will be the mean of the 7 day "average pain in your bladder over the last 24 hours" scores from the 7 reported days prior to Treatment 1 Day 1. Similarly, a patient's baseline daily worst pain NRS will be the mean of the 7 day "worst pain in your bladder over the last 24 hours" scores from the 7 reported days prior to Treatment 1 Day 1. Baseline average daily pain and average worst pain will only be calculated if the information is collected for *any* 5 consecutive days in the 7 days prior to Day 1 (i.e., Day -7 to Day -1). If less than 5 consecutive days are available, the baseline score will be set to missing.

Average daily pain NRS and daily worst pain NRS will be summarized for each week post- randomization. Patients are scheduled to have two IP insertion in Treatment 1 period and then Follow-Up visit. However, if a patient receives only one IP insertion in the study the follow up visits follow after the IP removal.

Table 17.2.1–1, presents for patients that receive more than one IP insertion, in days from first IP insertion within each treatment period the days to be included in each weekly summary. For patients that only receive one IP, Table 17.2.1-1 also presents in days from this IP insertion the days to be included in each weekly summary. For the postbaseline weeks that do not cover IP insertion or removal, a patient will be included in each weekly summary if they have at least 5 consecutive days of information within the summary week presented in Table 17.2.1-1. For the week intervals that cover IP insertion or removal a different rule is applied. For assessment weeks where there is IP insertion, the day of insertion and the two days after the day of insertion will not be included in the weekly average summary. The summary for such a week will be based on all available values, provided there are at least three days of daily assessments to be summarized (the days that are to be removed will be considered in the 5 day criteria). In contrast, for the week where IP removal occurs, the IP removal date and the day after the IP removal will be removed from the weekly average summary. The summary for such a week will be based on all available values provided there are at least three daily assessments to be summarized (the days that are to be removed will be considered in the 5 day criteria). The rational for excluding these IP insertion and removal dates is to reduce the impact of pain or pain medication that is related to the procedure rather than the disease under consideration.

Table 17.2.1–1 presents the weekly pain assessment windows.

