5.6 Treatment Regimen and Dosing

5.6.1 Treatment 1

Eligible patients will be randomized on Randomization/Day 0 to receive Treatment 1, LiRIS 400 mg/LiRIS 400 mg; LiRIS Placebo/LiRIS Placebo or LiRIS Placebo/LiRIS 400 mg (Section 5.4). Patients will have the Treatment 1, 1st IP inserted on Randomization/Day 0 and removed on Day 14. On the same day, following the 1st IP removal, the 2nd IP (LiRIS 400 mg or LiRIS Placebo) will be inserted and subsequently removed on Day 28. Patients will be followed for 20 weeks post IP removal for additional safety and efficacy assessments. In the event that a patient does not receive Treatment 2, they will exit the study at Treatment 1 Week 20 Follow-up Visit.

5.6.2 Treatment 2

All patients will receive LiRIS 400 mg for their second treatment. Patients may request, qualify, and receive Treatment 2 IP from Week 4 Follow-up until Week 20 of Treatment 1. In the event that the Treatment 2 IP cannot be inserted on the day of qualification, Treatment 2 may be rescheduled within 14 days of qualification. The LiRIS will be inserted on Treatment 2/Day 0, and will be removed on Day 14. Patients will be followed for 4 weeks post-removal and will be exited from the study.

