8.5 Unscheduled Visits

Unscheduled visits can be performed if safety concerns arise and at the discretion of the investigator. Additional examinations may be performed as necessary to ensure the safety and wellbeing of patients during the study. eCRFs will be completed for each unscheduled visit.

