17.2.2 Void Data Derivations

• For baseline and posttreatment visits, analyses on void diary efficacy variables will be based on the diary data collected during a 3-day interval for each visit. Each 3-day interval consists of 3 consecutive 24-hour periods, with the first period starting from the time of the first urinary episode on the first of the 3 days.

- A valid diary day is defined as any of the three 24-hour periods with 2 or more urinary episodes. Data collected from a 24-hour period with less than 2 urinary episodes (i.e., an invalid diary day) will be set to missing.
- For baseline and posttreatment visits, the 3-day diary will be determined based on the following algorithm:
 - Apply visit windows defined in Section 17.1, which are based on days from the date of study first treatment in each treatment period.
 - Determine the time of the first urinary episode that is within the visit window (in the example below, 7:30 am on April 3). Count forwards for 3 consecutive days. Note: the last 24-hour period should end within the window, i.e., prior to or on the last day specified in the window definition; otherwise, the 24-hour data will not be used for the corresponding window. For baseline diary data, the urinary episodes that occurred on the day of first IP insertion but before the IP insertion time will be counted as baseline diary data.
 - Using the example below, the first 24-hour time period starts from 7:30am on April 3 and ends at 7:29 am on Apr 4. The second 24-hour time period starts from 7:30am on Apr 4 and ends at 7:29 am on Apr 5. Note that this 24-hour is considered as an invalid diary day since it has just one episode during the 24 hours. The third or the last 24-hour time period starts from 7:30 am on Apr 5 and ends at 7:29 am on Apr 6.
 - At least one valid 24-hour diary day within the window is required for the visit. Otherwise, the 3-day diary data will be missing for the visit.

17.3 **REPEATED OR UNSCHEDULED ASSESSMENTS OF SAFETY PARAMETERS**

If a patient has repeated assessments before the start of the first treatment, the results from the final non-missing assessment made prior to the start of the study treatment will be used as baseline.

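### SAP 17.1 lets an unscheduled value taken after device removal replace the scheduled removal-visit value in the by-visit safety summaries

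*SAP*

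**What the plan says.** SAP 17.1 defines "the derived visits for efficacy (excluding efficacy based on daily pain diary) and safety analyses" by windows, each running over "target day of current visit + target day of previous visit)/2+1] to [(target day of current visit + target day of next visit)/2". When a window holds more than one visit, the rule is: "If a patient has 2 or more visits within the same visit window, the last visit with a nonmissing value will be used". The scope is wide: "If not stated otherwise, all by visit analysis will be using the visit windows specified above". The study-day origin is also set there: "the date of first IP insertion will be considered as Treatment 1 Day 1". Protocol Day 14 is therefore study day 15, and protocol Day 28 is study day 29.

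Protocol 5.6.1 takes the first device out on Day 14 and replaces it at that visit: "following the 1st IP removal, the 2nd IP (LiRIS 400 mg or LiRIS Placebo) will be inserted and subsequently removed on Day 28". Protocol 5.6.2 removes the single Treatment 2 device on its Day 14.

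Protocol 8.5 states: "Unscheduled visits can be performed if safety concerns arise and at the discretion of the investigator". It also requires eCRFs for these visits, so their data reach the database. The heading of SAP 17.3 covers repeated or unscheduled safety assessments, but its only rule opens with "If a patient has repeated assessments before the start of the first treatment" and settles the choice of baseline. It gives no rule for unscheduled values after baseline.

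**The concern.** The removal visit is the planned reading at the end of each device period. If a later unscheduled value falls in the same window, the SAP discards the scheduled value and reports the later one under the removal-visit label. For the last device of each treatment period, the later value is off-device. For the first Treatment 1 device, it is taken under the second device, which in the Placebo/LiRIS 400 mg group is a different treatment.

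What is at stake is whether the by-visit safety summaries describe the exposure that their labels imply. The SAP respects removal as a boundary elsewhere. SAP 12.1 counts lidocaine-related events only up to the day after removal, and SAP 17.2.1 drops pain scores around insertion and removal from the weekly means. The visit windows make no such distinction.

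**Working it through.** The plan states no figure on this point, so there is none to reproduce. The check applies the SAP 17.1 formula to the removal days.

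**Inputs.** Removal falls on study days 15 and 29 in Treatment 1 and on study day 15 in Treatment 2 (Protocol 5.6 with the SAP 17.1 day count). Table 17.1-1 and Protocol Table 1 are not shown, so neighbouring target days are assumed and ranged. Removal is taken to occur on its target day.

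**Formula.** Lower bound = (current + previous)/2 + 1. Upper bound = (current + next)/2. The tail after removal is upper − current = (next − current)/2. It holds at least one whole day whenever the next target is 2 or more days later, and it does not depend on the previous target.

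**Treatment 1, study day 29 (second device out), previous target 15.** Lower bound = (29 + 15)/2 + 1 = 23.
- Next target 36 (1 week): upper = 65/2 = 32.5. Days 30–32 are off-device: 3 of 10 days.
- Next target 43 (2 weeks): upper = 72/2 = 36. Days 30–36: 7 of 14.
- Next target 57 (4 weeks): upper = 86/2 = 43. Days 30–43: 14 of 21.

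**Treatment 2, study day 15 (device out), previous target 1.** Lower bound = (15 + 1)/2 + 1 = 9.
- Next target 22, 29 or 43: upper = 18.5, 22 or 29. The tail is again 3, 7 or 14 days.

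**Treatment 1, study day 15 (devices exchanged), previous target 1.** Lower bound = 9.
- Next target 22 or 29: upper = 18.5 or 22. The tail is days 16–18 or 16–22, spent under the second device in every group. Only Placebo/LiRIS 400 mg (planned N = 19) changes treatment at this point.

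**Which outputs use the windowed value.**
- SAP 12.2 (laboratory), 12.3 (vital signs) and 12.5.1 (PVR) give descriptive statistics by visit. These are exposed.
- The laboratory shift table in SAP 12.2 runs from baseline to end of study only, so it would not show a displaced removal-visit value. No worst on-device summary is visible.
- Protocol 6.5.4 takes vital signs before invasive procedures, so the scheduled removal-visit reading is on-device. Protocol 6.5.5 does urinalysis at all clinic visits. Whether blood tests or PVR are scheduled at removal cannot be confirmed from the text.

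**Effect of one replacement.** If the later value differs from the scheduled one by d and all planned patients contribute, the group mean moves by d/38 = 0.026d (N = 38) or d/19 = 0.053d (N = 19). A minimum or maximum can move by as much as d.

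**The case against.** The strongest reply is that keeping the last value in a window is a common convention, is fixed in advance, is identical across groups and feeds no safety hypothesis test. The primary endpoint is outside these windows, because pain-diary data are excluded. Safety events are also kept elsewhere. Abnormal laboratory findings can be adverse events (Protocol 9.1.1), treatment-emergent events are tabulated by period at greatest severity (SAP 12.1), and reported laboratory values go to listings (SAP 17.9). Physical examination and cystoscopy abnormalities are summarised by treatment phase (SAP 12.5.2 and 12.5.3). All of this stands and limits the point to the by-visit descriptive summaries.

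A reader might infer something stronger: that the rule hides abnormal findings and systematically understates on-device safety. The documents do not support that, for three reasons.
- Selection of the last value has no built-in direction. A normal removal-visit value can be displaced by an abnormal one from a visit for a new problem, just as an abnormal value can be displaced by a resolved one. Protocol 8.5 does not say that unscheduled visits are rechecks of removal-day values, or which tests they repeat.
- The visible by-visit laboratory, vital-sign and PVR outputs are descriptive statistics, not counts of abnormal patients, so a fall in an abnormal percentage cannot be claimed.
- At Day 15 of Treatment 1 the tail is on-device, so no off-device value enters by that route.

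The objection leaves the labelling problem in place. A convention that ignores both scheduling and removal can put a value under a visit that describes a different exposure.

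**Conclusion.** The point holds as a limited defect in data handling. The final-removal windows of both treatment periods extend past removal by 3, 7 or 14 days under next targets 1, 2 or 4 weeks later, and some overrun follows from the formula for any next target at least 2 days away. An unscheduled value in that tail replaces the scheduled one in the by-visit means and extremes of vital signs, and of any laboratory or PVR values scheduled at removal. In Placebo/LiRIS 400 mg, a value under LiRIS can also be reported as the end of the placebo device.

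The replacement is conditional on an unscheduled visit inside the tail that records the same parameter. The documents give no rate for this, so neither its frequency nor its net direction can be stated. The exact windows rest on a table that is not shown. Adverse event tables, listings and by-phase findings are unaffected. The change is worth making because it is cheap, not because a safety conclusion is shown to be wrong.

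**What to change.** In SAP 17.1:
- Use the scheduled visit's value when it is present; otherwise use the nonmissing value closest to the target day.
- Do not let a value taken after removal stand for a removal visit. Apply this to both Treatment 1 removals and to the Treatment 2 removal.
- Start the next window the day after removal. Closing the Day 15 window alone would leave days 16–22 unassigned if the next target is day 29.

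In SAP 17.3, extend the rule to post-baseline unscheduled values and keep them in the listings. Optionally, add a summary of the worst on-device value by treatment group.

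The cost is SAP wording and minor programming (a scheduled/unscheduled flag and a comparison with the actual removal date), with no new data. A patient with no on-device value in the removal window would show as missing there instead of being filled with an off-device value. Protocol 7.5 requires SAP deviations after database lock to be documented, so the change belongs in the SAP before lock.

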6.5.8 Cystoscopic Examination

All patients will undergo a cystoscopic examination on the days of Insertion of the IP to rule out the presence of any bladder or urethra anatomical feature that, in the opinion of the investigator, might prevent the safe placement, indwelling use, or removal of IP, such as bladder fistulae or stone. In addition, prior to the intial IP insertion on Day 0, the presence of HLs will be confirmed. If during the cystoscopic exam, the investigator discovers an abnormality that would prevent the safe placement, indwelling use, or removal of the IP, the patient will not receive treatment and will be withdrawn from the study.

A brief cystoscopic examination for safety purposes will also be conducted on all patients at the Treatment 1 and Treatment 2 Day of Removal Visits (see Table 1).

During each cystoscopy, the investigator will count the number of lesions visible while performing the bladder scan for bladder mapping.

Investigators may recommend that the patient take pain medication up to 6 hours prior to the cystoscopic procedure and continuing for 24 hours after the procedure to minimize patient anxiety and discomfort.

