7.2.1 Primary Efficacy Variables

The primary efficacy variable is the change in average daily bladder pain NRS at Week 4 Follow-up Visit post removal of 2nd IP of Treatment 1 as compared to study baseline.

The average daily pain NRS of the preceding 7 days (at least 5 consecutive days) will be calculated and used to calculate baseline and change from baseline at each scheduled visit. If no data are available for at least a period of 5 consecutive days, that average will be considered missing for that patient. The primary timepoint is 4-week follow up after removal of the 2nd IP of Treatment 1. If there is no valid Week 4 Follow-up NRS assessment and there is a valid Week 2 or 3 Follow-up NRS assessment, the Week 4 Follow-up value will be imputed using the latest of the 2 values that is available (ie, Week 2 or 3 Follow-up).

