11.0 EFFICACY ANALYSES

The efficacy analyses will be primarily based on the mITT Population with selected tables being repeated using the PP population. Unless stated otherwise, baseline for efficacy is defined as the last non-missing efficacy assessment prior to first Treatment 1 IP insertion. All statistical tests will be 1-sided hypothesis tests performed at the 5% level of significance for main effects. All confidence intervals will be 2-sided 90% confidence intervals, unless stated otherwise.

11.1 **PRIMARY EFFICACY PARAMETER(S)**

The primary efficacy measure is the 7-day mean of the average daily bladder pain NRS (See Section 17.2.1 for definition of average daily bladder pain score).

The primary efficacy variable is the change from baseline to Week 4 Follow-Up post removal of the last IP in Treatment 1 period, using the 7-day mean of the average daily bladder pain NRS score. Patients are scheduled to have two IP insertion in Treatment 1 period and then a Week 4 Follow-Up visit. However, if a patients receives only one IP insertion in the study and has Week 4 Follow-Up assessment, it will be considered in the analysis.

The baseline 7-day mean daily average NRS score will be derived using the diary information from Day -7 to Day -1. In contrast, for patients that receive two IP insertion, the Week 4 Follow-Up mean 7-day average daily pain score will be derived from data collected from Day 50 to Day 56 from date of 1nd IP insertion or Day 36 to Day 42 for patients that receive just one insertion during Treatment 1 period. The mean baseline NRS will be derived if there are at least *any* 5 consecutive valid assessments within the 7-day assessment window (i.e., for baseline it would be day -7 to day -1). If the data that is available is for less than 5 consecutive days, as described above, then the value will be considered missing for that patient. Similarly, the Week 4 Follow-Up NRS will be derived if there are at least *any* 5 consecutive valid assessments within the 7-day assessment window (Day 50 to Day 56 for patients that received two insertion or Day 36 to Day 36 to Day 36 to Day 42 for patients that received just one IP in Treatment 1).

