12.5.3 Cystoscopic Exam

All patients will undergo a cystoscopic examination on the days of insertion and removal of the IP, Treatment 1 Week 4 Follow-up and at study exit if the patient does not continue into Treatment 2 period. Abnormal findings will be summarized by treatment phase.

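### The SAP's procedure-day exclusion omits the Week 4 Follow-up cystoscopy: an on-time visit affects only the following week's mean, but an early visit puts one or two affected days into the primary mean

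*SAP*

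**What the plan says.** SAP 17.2.1 has two rules for weekly pain means after baseline.

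- **Weeks with device handling.** At insertion, "the day of insertion and the two days after the day of insertion will not be included in the weekly average summary". At removal, "the IP removal date and the day after the IP removal will be removed from the weekly average summary". Such a week needs only three daily assessments. The reason given is: "The rational for excluding these IP insertion and removal dates is to reduce the impact of pain or pain medication that is related to the" intervention itself.
- **All other weeks.** "For the postbaseline weeks that do not cover IP insertion or removal, a patient will be included in each weekly summary if they have" five consecutive days of data. No day is dropped for a procedure.

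SAP 12.5.3 schedules cystoscopy "on the days of insertion and removal of the IP, Treatment 1 Week 4 Follow-up and at study exit", the last for patients who do not go on to Treatment 2. Protocol 6.5.8 lets investigators recommend that patients "take pain medication up to 6 hours prior to the cystoscopic procedure and continuing for 24 hours after the procedure". Under Protocol 6.5.12 the diary is preferably completed at the end of the day and covers the last 24 hours, so the visit-day entry includes the cystoscopy.

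The two documents anchor the primary week differently. In SAP 11.1 the Week 4 mean for a patient with two devices is "derived from data collected from Day 50 to Day 56 from date of 1nd IP insertion"; with one device it is Days 36 to 42. Protocol 7.2.1 uses "The average daily pain NRS of the preceding 7 days (at least 5 consecutive days") at each scheduled visit. Protocol 6.5.12 adds that, if a visit is rescheduled, the required run of diary days must lie in the seven days before the rescheduled date.

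**The concern.** The SAP accepts that pain or medication from an intravesical procedure can distort a diary score and removes those days. The Week 4 Follow-up cystoscopy escapes the rule only because no device is inserted or removed. The exit cystoscopy needs no such rule, because the diary stops the day before the Exit Visit. That leaves Week 4 Follow-up as the one cystoscopy listed in SAP 12.5.3 whose diary days are kept.

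Scores are exposed in two places. One is the weekly mean that follows the visit, which enters the by-week ANCOVA of SAP 11.1.1. The other is the primary Week 4 mean, if the visit takes place before the fixed window has closed. Besides scheduling, early removal of the second device can cause this: SAP 11.1 counts Week 4 Follow-up from the last removal but fixes the diary days from the first insertion. An affected primary mean would also enter the per-protocol and no-imputation analyses and the MMRM.

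**Working it through.** **Inputs.** First insertion is Day 1 (SAP 17.1), so SAP day = protocol day + 1. The second device is removed on protocol Day 28 (Protocol 5.6.1). Difference 1.152, SD 1.67, 36 versus 18 patients, one-sided 0.05, stated power 76% (SAP 15.0).

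**The plan's own figures.**
- Power: SE = 1.67 × √(1/36 + 1/18) = 0.482; noncentrality = 1.152 / 0.482 = 2.39 on 52 df; power = 76.2%. This reproduces 76%.
- Two devices: removal on Day 29; Week 4 visit on 29 + 28 = Day 57; the seven days before are Days 50 to 56, as in the SAP.
- One device: removal on Day 15; visit on Day 43; the seven days before are Days 36 to 42, also as in the SAP.

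The SAP and protocol windows therefore agree when the visit is on time.

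**Days affected by visit date.** I assume the visit day and the next day are affected, as in the SAP's removal rule. The following week is taken as Days 57 to 63. This is inferred, because Table 17.2.1-1 is not shown.

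| Week 4 visit | Affected days in primary window (50–56) | Affected days in next week (57–63) |
|---|---|---|
| Up to 3 days late | 0 | 2 |
| On time (Day 57) | 0 | 2 (Days 57, 58) |
| 1 day early (Day 56) | 1 (Day 56) | 1 (Day 57) |
| 2 to 7 days early | 2 | 0 |

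Patients who receive the Treatment 2 device at the Week 4 visit leave Treatment 1 that day and do not contribute to the right-hand column.

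**Size for one affected patient.** If procedure pain adds d points on two of seven days, the weekly mean rises by s = 2d/7. For d = 1, 2 and 3, s = 0.29, 0.57 and 0.86. The values of d are assumptions; the documents give none.

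**Size for the comparison, early visits equally common in all arms.** With a share f of early visits, each group mean shifts by f × s and the SD becomes √(1.67² + f(1 − f)s²).
- f = 10%, d = 1: shift 0.03, SD 1.67, power 76.1%.
- f = 50%, d = 3: shift 0.43, SD √(2.789 + 0.25 × 0.735) = 1.72, power 73.9%.

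The shift is the same in each arm, so the expected difference does not move.

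**Size if early visits differ by arm.** The difference shifts by (difference in share) × s, from 0.10 × 0.29 = 0.03 to 0.20 × 0.86 = 0.17.

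**Test of the remedies.** Dropping the cystoscopy day and the next from Days 50 to 56 leaves five days when the visit is 3 to 6 days early, but the longest run is only 3 or 4. The five-consecutive-day rule would then set the value to missing. Ending the window on the day before the actual visit leaves no affected day. In the following week, dropping two days after an on-time visit leaves five.

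**The case against.** The strongest reply is that the primary endpoint is safe whenever the visit is on time or late, and nothing in the documents shows that early visits are common. The permitted visit windows would be in Protocol Table 1 and SAP Table 17.1-1, neither of which is shown. The following week is a minor analysis: it is not the primary timepoint, the MMRM stops at Week 4, and the primary imputation uses Week 2 or 3. All arms have the same blinded cystoscopy at the same visit, so a common shift cancels. The SAP's exclusion can also be read as aimed at device handling, which makes its extension a refinement. All of this stands, and it limits the point's importance.

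A reader might divide 0.29 to 0.86 by 1.152 and infer that 25% to 74% of the target effect is at risk. The documents do not support that, because it compares a shift in one patient's mean with a difference between group means. A reader might also infer that improvement is understated. That is plausible if pain dominates, but the analgesia allowed around cystoscopy could lower scores, so the net direction is not known.

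The reply does not remove the mismatch between a window fixed by day count and one tied to the actual visit. Equal timing across arms is also not assured: the grounds for early removal in Protocol 5.6.3 include patient request and signs of lidocaine toxicity, which could differ by arm.

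**Conclusion.** The gap is real and its likely effect is small. For an on-time visit the primary mean is unaffected, and only the next weekly mean carries procedure days. For a visit before Day 57, one or two affected days enter the primary mean under SAP 11.1, and the protocol's anchor would have kept them out.

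The size cannot be fixed from the documents, since neither the share of early visits nor the procedure pain is given. Assuming 1 to 3 points on two days and 10% to 50% early visits, equal timing across arms leaves the expected difference unchanged and costs at most about 2.3 points of power (76.2% to 73.9%). An imbalance of 10 to 20 percentage points in early visits would shift the difference by about 0.03 to 0.17, against a planned 1.152. The statement about the following week rests on its inferred window. The change is worth making because it applies the SAP's own principle, restores the protocol's anchor and is cheap.

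**What to change.** 1. **SAP 11.1.** Use no pain score from the actual Week 4 Follow-up visit day onward in the primary mean. When the visit is early, take the seven days ending the day before it, as the protocol does, and keep the five-consecutive-day rule. Apply the same to the one-device window.
2. **SAP 17.2.1.** Extend the removal-day exclusion (the day and the day after) to the Week 4 Follow-up cystoscopy for the following weekly mean. Carry over the existing minimum of three daily assessments. Otherwise one missed entry among the five remaining days would make that week missing.
3. **SAP 11.1.1.** State which weekly windows the MMRM uses for early attenders. A visit on Day 54, for example, gives a Week 4 window of Days 47 to 53, which overlaps Week 3 if that week is Days 43 to 49 (inferred).

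The cost is SAP wording and programming, with no new data. The following weekly mean loses up to two days, and for early attenders the Week 4 window moves by a few days and shares some scores with Week 3.
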